9.1.2 Schedule of Assessments

The schedule of assessments is presented in [Table 9-1](#).

Table 9–1 Schedule of Assessments

Visit	Screening Phase		Randomisation Phase (Treatment Period)								Follow-Up ¹		
	Screening (D -28 to D -1)		1 (Baseline)	2	3	4	5	6	7	8 (EOT)	9	10	11 (FU)
Week/Day	Screen Visit 1	Screen Visit 2 (Visit 1 + 3-7 days)	D 1	D 8 (±1 D)	W4 (±2 D)	W8 (±2 D)	W12 (±2 D)	W16 (±2D)	W20 (±2 D)	W24 (±2 D)	W28 ² (±2 D)	W32 ² (±2 D)	W36 (±2 D)
Written informed consent	X												
Demographics	X												
Medical/surgical history	X												
Inclusion/exclusion criteria	X												
Androgen deficiency symptom checklist	X												
Randomisation			X										
Full general physical exam and prostate exam and breast exam	X						X			X			
Limited physical exam³			X	X	X	X		X	X				X
Vital signs ⁴ ; height (Visit 1 only)	X		X	X	X	X	X	X	X	X			X
12-Lead ECG	X		X		X	X	X			X			
Specialised chemistry: morning cortisol, TSH, FT4, prolactin, iron, transferrin ⁵	X												
25 hydroxy vitamin D			X										
Clinical laboratory tests: haematology, blood chemistry, eGFR by Cockcroft-Gault formula, dipstick urinalysis ⁶ and PSA ⁷	X		X	X	X	X	X	X	X	X			X
Cardiometabolic parameters 1: HbA1c, fasting lipids (total cholesterol, LDL, HDL, triglycerides) ⁷	X				X		X			X			X
Cardiometabolic parameters 2: Fasting glucose and insulin, hs-CRP, HOMA-IR Bone turnover markers^{7,8}			X				X			X			X
Sex hormones 1: testosterone (total), oestradiol (total), LH	X ^{9, 11}	X ^{9,10, 11}	X ¹¹	X ¹¹	X ¹¹	X ¹¹	X ¹¹	X ¹¹	X ¹¹	X ¹¹			X
Bioavailable testosterone, SHBG			X ¹¹	X ¹¹	X ¹¹	X ¹¹	X ¹¹	X ¹¹	X ¹¹	X ¹¹			X
Sex hormones 2: FSH			X	X	X	X	X	X	X	X			X
DHT, inhibin A and B			X				X			X			X
Semen quality analysis ¹²			X				X		X				
Semen PK samples ¹³										X			
Plasma PK samples ¹⁴							X			X			
Hip and waist measurement			X				X			X			

Visit	Screening Phase		Randomisation Phase (Treatment Period)								Follow-Up ¹		
	Screening (D -28 to D -1)		1 (Baseline)	2	3	4	5	6	7	8 (EOT)	9	10	11 (FU)
Week/Day	Screen Visit 1	Screen Visit 2 (Visit 1 + 3-7 days)	D 1	D 8 (±1 D)	W4 (±2 D)	W8 (±2 D)	W12 (±2 D)	W16 (±2D)	W20 (±2 D)	W24 (±2 D)	W28 ² (±2 D)	W32 ² (±2 D)	W36 (±2 D)
Body composition using bioimpedance ¹⁵ (by impedance)			X				X			X			
Actigraphy ¹⁶			X				X			X			X
Grip strength			X		X	X	X			X			X
PROs: IIEF, BFI, PROMIS SexFS, PROMIS Fatigue Short Form, PGI-S		X ¹⁷	X		X	X	X			X			X
PROs: SF-36			X				X			X			X
DEXA	X ¹⁸									X ¹⁸			

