If the subject decides to completely withdraw from the study (refuses any further study participation or contact) all study participation for that subject will cease and data to be collected at subsequent visits will be considered missing.

The investigator must also contact the IRT to register the subject's discontinuation from investigational treatment.

If study drug is discontinued prior to the subject's completion of the study, the reason for the discontinuation must be documented in the subject's medical records and entered on the appropriate case report form (CRF) page.

If the subject temporarily discontinues study drug because of AE or SAE or other relevant issue, investigator may restart if considered medically safe and in discussion with the Medical Monitor.

Investigational treatment MAY be permanently discontinued under the following circumstances:

1. Significant worsening of lower extremity oedema (demonstrated by use of the same technique of evaluation for comparison over time and which is not due to local pressure /venostasis effects such as may be caused by socks or other clothing).
2. Significant worsening of obstructive urinary symptoms

Investigational treatment MUST be permanently discontinued under the following circumstances:

3. Total testosterone \geq 1500ng/dL (52 nmol/L) at any two consecutive scheduled visits during the study
4. Liver laboratory values of:
 - ALT or AST >5 times the ULN

If the increase in ALT or AST, is associated with normal bilirubin and ALP, the medical evaluation of withdrawing a patient can be made on a repeat AST/ALT test taken within 48 hours. (Repeated parameters should include: ALT, AST, Alkaline phosphatase and total bilirubin). The subject should interrupt study drug until the repeat liver enzymes are available. If repeat liver parameters are all within the normal range, dosing may be continued. If not normalised the subject should be permanently discontinued.

or

- ALT or AST >3 times the ULN and bilirubin total >2 times ULN or International Normalised Ratio (INR) >1.5 or the appearance of worsening fatigue, nausea, vomiting, right upper quadrant pain/tenderness, fever, rash, or eosinophilia.
 - A hepatic event leading to subject discontinuation should be followed up until event resolution, or becomes not clinically significant
5. Any of the following laboratory abnormalities:
 - Renal function values that require discontinuation:

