- Discontinue investigational treatment for a subject if individual serum creatinine increases $\geq 50\%$ compared to Baseline (and is considered clinically significant), or in the event of treatment emergent proteinuria (albumin:creatinine ratio [ACR] >300 mg/g or >30 mg/mmol; protein:creatinine ratio [PCR] ≥ 500 mg/g or >50 mg/mmol). (Creatinine can be repeated once within 7 days of initial alert. Study drug administration should be suspended during this time and resumed only if repeat creatinine is back to pre-alert level)
 - A renal event leading to subject discontinuation should be followed up until event resolution (serum creatinine within 10% of Baseline, protein-creatinine ratio within 50% of Baseline), stabilises or becomes not clinically significant, or is assessed as being chronic.
6. Subject missed 4 or more consecutive study drug dosing.
 7. Development of prostate cancer or PSA increase more than 1.4 ng/ml above Screening level. It is recommended that in these cases subjects undergo urologic consultation.
 8. Haematocrit $>54\%$ (Hematocrit can be repeated once within 7 days of initial alert. Study drug administration should be suspended during this time and resumed only if repeat hematocrit is under 54%)
 9. Development of sleep apnoea.
 10. Development of cardiovascular event (significant arrhythmia acute myocardial infarction, brain stroke, transient ischemic attack, unstable angina, congestive heart failure).
 11. Emergence of the following adverse events:
 - Absolute QTcF >500 msec, or a rise of QTcF of ≥ 60 msec above baseline confirmed by triplicate ECG measurements.
 12. Pregnancy in female sexual partner of the male study subject, occurring after the start of study treatment.
 13. Fragility bone fracture.
 14. Breast cancer.

Procedures for handling patients incorrectly enrolled or randomized

Subjects who fail to meet the inclusion/exclusion criteria must not be enrolled or randomized. If a subject not meeting the study criteria is randomized in error, a discussion must occur between the Medical Monitor and the investigator regarding whether to continue or discontinue the subject from the study. If agreement is reached, the subject should complete the study unless there are safety concerns or if the subject withdraws the consent.

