12.3.1 Clinical Laboratory Tests

Blood Chemistry

Sodium, potassium, chloride, bicarbonate/CO₂, blood urea nitrogen, creatinine, fasting glucose, albumin, alkaline phosphatase, AST, ALT, PT/INR, total bilirubin, total protein, calcium, lipid panel (total cholesterol, LDL, HDL, triglycerides) and PSA will be measured.

eGFR will be calculated based on Cockcroft-Gault formula:

$$\text{eGFR} = ((140 - \text{Age}) / (\text{SerumCreat})) * (\text{Weight} / 72)$$

Haematology

Haemoglobin, white blood cell (WBC) count with differentials (monocytes, eosinophils, basophils, neutrophils, lymphocytes) as an absolute value, red blood cell (RBC) count and platelet count will be measured.

Urinalysis

Specific gravity, pH, semi-quantitative “dipstick” evaluation of glucose, protein, bilirubin, ketones, leukocytes and blood will be measured.

A microscopic examination including RBC and WBC will be performed only when dipstick evaluation is positive for WBC and/or blood or protein. A midstream urine sample (about 30 mL) will be obtained, in order to avoid contamination with epithelial cells and sediments, and allow proper assessments.

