8.7.2 Laboratory evaluations

8.7.2.1 Clinical laboratory

Haematology, blood chemistry, and urinalysis assessments will be conducted at Screening, Baseline, each visit during the treatment phase and Week 36.

The following laboratory parameters will be assessed:

- Blood chemistry
 - Sodium
 - Potassium
 - Chloride
 - Bicarbonate/CO₂
 - Blood urea nitrogen

-
- Creatinine
 - Fasting Glucose
 - Albumin
 - Alkaline phosphatase
 - AST
 - ALT
 - GGT
 - PT/INR
 - Total bilirubin
 - Total protein
 - Calcium
 - Lipid panel (total cholesterol, LDL, HDL, triglycerides)
 - PSA
 - eGFR (calculated based on Cockcroft-Gault formula)
 - eGFR (derived from 4-v MDRD)
 - Haematology
 - Red Blood Cell Count [RBC]
 - White Blood Cell Count [WBC]
 - Neutrophils
 - Lymphocytes
 - Monocytes
 - Eosinophils
 - Basophils
 - Haemoglobin
 - Haematocrit
 - Platelets
 - Urinalysis
 - Specific gravity
 - pH
 - Protein
 - Bilirubin
 - Glucose
 - Blood
 - Ketones
 - Leukocytes

For the purposes of summarisation in both the tables and listings, all clinical laboratory data will be reported in Standard International (SI) units.

If a lab value is reported using a nonnumeric qualifier e.g., less than (<) a certain value, or greater than (>) a certain value, the given numeric value will be used in the summary statistics, ignoring the nonnumeric qualifier.

Descriptive statistics will be presented for quantitative clinical laboratory parameters for each treatment regimen and time-point. Similarly, changes from baseline (and changes from screening for selected renal parameters; creatinine, urea, and glomerular filtration rate) will be summarised.

The change from baseline in each renal parameter to Week 24 will also be analysed via MMRM in the same manner as the change from baseline in total testosterone (see Section 8.6.3.1).

Values outside the normal range will be categorised as H (above the normal range) or L (below the normal range) based on the laboratory's reference range and these will be flagged in the individual data listings along with the Investigator's assessment.

In addition boxplots of observed values by treatment and visit will be generated for the below lab parameters:

- Hematocrit
- Hemoglobin
- Creatinine
- PSA

Qualitative urinalysis parameters (e.g protein, glucose and blood) will only be listed.

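### Proteinuria above a urine ACR or PCR limit must end treatment, but the Protocol and SAP plan no assay of either ratio and no trigger for ordering one

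*Protocol*

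**What the plan says.** **The rule.** Protocol Section 9.3.7 introduces its list with "Investigational treatment MUST be permanently discontinued under the following circumstances". Item 5, on renal function, has two limbs: a rise in serum creatinine from Baseline, and "treatment emergent proteinuria (albumin:creatinine ratio [ACR] >300 mg/g or >30 mg/mmol", with a corresponding PCR limit. A renal event that leads to discontinuation is then followed until one of several end points. One of these is resolution, which includes "protein-creatinine ratio within 50% of Baseline".

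**The tests.** The laboratory row of Protocol Table 9-1 covers "haematology, blood chemistry, eGFR by Cockcroft-Gault formula, dipstick urinalysis" and PSA. Section 12.3.1 confines urinalysis to specific gravity, pH and a semi-quantitative dipstick: "evaluation of glucose, protein, bilirubin, ketones, leukocytes and blood will be measured". The follow-on test is conditional: "A microscopic examination including RBC and WBC will be performed only when dipstick evaluation is positive for WBC and/or blood or protein". Albumin and creatinine appear in Section 12.3.1 only under blood chemistry ("blood urea nitrogen, creatinine, fasting glucose, albumin, alkaline phosphatase").

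**The analysis.** SAP 8.7.2.1 repeats the dipstick items and states: "Qualitative urinalysis parameters (e.g protein, glucose and blood) will only be listed". The renal parameters it summarises and models are creatinine, urea and glomerular filtration rate.

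**The concern.** A mandatory stopping rule should be decidable from data that the plan produces. Here a site that follows the schedule exactly never obtains a number to compare with the limit. Whether a man with protein in his urine is stopped then depends on whether his investigator orders a quantitative test that no text asks for, so the rule may be applied differently from site to site.

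Two features of the trial make this more than a drafting detail. Version 6.0 admits men with type 2 diabetes who use insulin and have HbA1c up to 10.5%, and no eligibility criterion sets a urine protein limit. Also, the SAP pays close attention to renal safety: a second eGFR formula, change from Screening, repeated-measures models of the renal parameters, and plots of creatinine change against blood pressure. None of these includes a quantitative measure of urine protein.

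**Working it through.** No sample size, power or error rate depends on this point. The check sets what the rule needs beside what the plan supplies.

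| Needed by Section 9.3.7 | Planned in Protocol or SAP |
|---|---|
| On-treatment urine ACR or PCR | None. Table 9-1 has no such row, and neither Section 12.3.1 nor SAP 8.7.2.1 lists one |
| Urine albumin, urine total protein and urine creatinine to form a ratio | None. The dipstick grades protein but includes no creatinine; albumin and creatinine are blood tests |
| An instruction on when to quantify | None. The only reflex after a positive dipstick is microscopy |
| Baseline PCR for the resolution criterion | None at Screening or Day 1 |
| Follow-up PCR after discontinuation | None. Visits 9 and 10 are by telephone; Visit 11 has dipstick only |
| Serum creatinine at Baseline and on treatment | Planned, so this limb can be applied |

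**Visit count from Table 9-1.** Dipstick urinalysis falls at Screening Visit 1, Visits 1 to 8 and Visit 11: 1 + 8 + 1 = 10. ACR or PCR: 0 of 10.

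**Could the list simply be incomplete?** Section 12.3.1 does omit haematocrit, which the trial clearly measures. The SAP list supplies haematocrit and adds GGT and a second eGFR, but still has no urine ratio. Outside Section 9.3.7, ACR and PCR appear only in the Protocol's abbreviation list.

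**A related mismatch.** Protocol Table 9-1 footnote 6 and Section 12.3.1 make a dipstick positive for protein a trigger for microscopy. SAP Table 1 footnote 6 names only white cells and blood.

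**Two side observations.** The provision for a repeat within 7 days names creatinine only, so the proteinuria limb has no stated confirmation step. The paired unit limits are also only roughly equal. The conversion factor in SAP 7.1.4.6 (0.011312 mg/dL per µmol/L) gives 0.11312 g of creatinine per mmol. Then 300 mg/g × 0.11312 = 33.9 mg/mmol, against the stated 30; and 500 mg/g × 0.11312 = 56.6 mg/mmol, against the stated 50. This affects no result now, but would matter once a ratio is reported in one unit.

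**The case against.** The strongest reply is that this is a missing instruction, not a rule that cannot work. Several parts of that reply stand.

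- **A screen exists.** Dipstick protein is scheduled at every on-site treatment visit. Section 12.1.4 foresees abnormal results that call for further diagnostic testing, so a ratio ordered for cause is compatible with the Protocol. A reader might infer that the rule is inoperable; the documents do not go that far. What is missing is the assay and its trigger, not the urine.
- **Treatment emergence can often be judged.** The ACR and PCR limits are absolute values, not changes. A man whose Screening and Day 1 dipsticks were negative and who later exceeds a limit can reasonably be called treatment emergent. It would be too strong to say that this can never be established without a Baseline ratio. The ambiguity is confined to men who were dipstick-positive before dosing or whose earlier albuminuria the dipstick missed. The documents give no number for either group.
- **The resolution rule has other exits.** Follow-up can also end when the event stabilises, is no longer clinically significant, or is judged chronic. The Baseline PCR matters only for men with a renal event leading to discontinuation, so counting all 268 planned men as affected would overstate the size.
- **Eligibility gives some protection.** Exclusion 22 (significant renal disease) and exclusion 25 (eGFR below 60 mL/min) apply, and the placebo arm gives a comparison between groups.
- **Proteinuria is not absent from the safety tables.** An abnormality that is clinically significant or leads to discontinuation is reported as an adverse event, and SAP 8.7.1 tabulates such events by regimen.
- **The laboratory manual might specify the assay.** Section 12.3 refers to it for further detail.

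These replies do not close the gap. For-cause testing is permitted but nowhere requested. The adverse event tables can count only the men whose proteinuria a site noticed and acted on. SAP 8.1.7 lists unscheduled visit results but does not tabulate them. Nothing in the Protocol or SAP says that the manual adds these assays.

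**Conclusion.** The point holds in a limited form. Section 9.3.7 sets a mandatory stopping criterion in terms of two urine ratios, and the Protocol and SAP plan neither ratio at any of the 10 visits with urinalysis, including Screening and Baseline. The proteinuria limb therefore cannot be applied from the planned tests and rests on each site's decision to order an unscheduled one.

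The serum creatinine limb, the efficacy analyses and the power are unaffected. The documents do not show that proteinuria would go undetected, that treatment emergence could never be judged, or that the renal safety report would be silent on it.

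The conclusion assumes that the laboratory manual, which was not available, does not add the assays. If it does, the remaining task is to say so in the Protocol and SAP. It should be corrected because it concerns patient safety and costs little.

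**What to change.** Reconcile Section 9.3.7 with Table 9-1 footnote 6, Section 12.3.1 and SAP 8.7.2.1. One way that uses only quantities the Protocol already names:

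1. In Section 12.3.1 and Table 9-1 footnote 6, add a spot-urine ACR and PCR on the same specimen when the dipstick is positive for protein, alongside the existing microscopy reflex.
2. Quantify both on the Day 1 urine for men not yet randomised. The Version 6.0 summary of changes refers to more than 100 patients already in the trial. No text says that urine was stored, so men already enrolled would rely on their baseline dipstick. If the 268 planned are enrolled, this means fewer than 268 − 100 = 168 Day 1 specimens.
3. Align SAP Table 1 footnote 6 with Protocol footnote 6 on protein as a microscopy trigger.
4. In SAP 8.7.2.1, tabulate by regimen the men who meet the Protocol's own proteinuria criterion, including results obtained outside scheduled visits.
5. Reconcile the paired unit limits in Section 9.3.7 with each other.

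If the sponsor prefers not to quantify, the same sections must be reconciled in another way. Which threshold or clinical rule applies is for the sponsor.

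**Cost:** a few assays on urine already collected, laboratory manual wording, a protocol clarification and one SAP table. No extra visit or specimen is needed. A reflex assay covers only men whose dipstick is positive, so the rule would still depend on the dipstick as its screen.

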9.3.8 Lost to Follow-up

All reasonable efforts must be made to locate subjects to determine and report their ongoing status. This includes follow-up with persons authorised by the subject. Lost to follow-up is defined by the inability to reach the subject after a minimum of three documented phone calls, faxes or emails, as well as a lack of response by the subject to one registered mail letter. All attempts should be documented in the subject's medical records. If it is determined that

the subject has died, the site will use permissible local methods to obtain the date and cause of death.

If the investigator's use of a third-party representative to assist in the Follow-Up Phase of the study has been included in the subject's informed consent, then the investigator may use a sponsor-retained third-party representative to assist site staff with obtaining subject's contact information or other public vital status data necessary to complete the Follow-Up Phase of the study. The site staff and representative will consult publicly available sources, such as public health registries and databases, in order to obtain updated contact information. If, after all attempts, the subject remains lost to follow-up, then the last known alive date as determined by the investigators should be reported and documented in the subject's medical records.

10 TREATMENT OF SUBJECTS

10.1 Identity of Study Treatment(s)

Details of the study treatments are presented in [Table 10–1](#).

Table 10–1 Study Treatments

Drug Name	BGS649	BGS649 matched placebo
Active ingredient	BGS649	Not applicable
Strength(s)	[REDACTED]	Not applicable
Dosage Form	[REDACTED]	c [REDACTED]
Route of administration	Oral	Oral
Mode of administration	With water	With water
Dose	[REDACTED]	[REDACTED]

10.1.1 Administration of Study Treatment(s)

[REDACTED]

10.2 Study Treatment Packaging and Labelling

10.2.1 Packaging

[REDACTED]

A unique medication number is printed on the label of each pack which corresponds to one of the treatment regimens. Investigator staff will identify the investigational treatment to dispense to the subject by contacting the IRT and obtaining the medication number(s). Records of subjects assigned medication numbers will be recorded in source documentation.

10.2.2 Labelling

Labels will comply with the legal requirements of each country and be printed in the local language. They will supply no information about the subjects.

10.2.3 Storage

[REDACTED]

10.2.4 Blinding and Randomisation of Study Treatment(s)

At Visit 1 (Baseline) all eligible subjects will be randomised via the IRT to one of the four treatment regimens [REDACTED] in a 1:1:1:1 ratio. After the interim analysis (see [Section 13.6](#)), if one or more of the BGS649 study arms is discontinued by the DMC, the dosing for that arm(s) will be stopped and no further randomisation to that arm will be performed. The remaining subjects will be randomised in a 1:1:1 ratio into remaining active arms: [REDACTED]

[REDACTED] The investigator or his/her delegate will contact the IRT after confirming that the subject fulfils all the inclusion/exclusion criteria. The IRT will assign a medication number to the subject, which will be used to link the subject to a treatment regimen and will specify a unique medication number on the label of investigational treatment to be dispensed to the subject. The randomisation number will not be communicated to the caller.

The randomisation numbers will be generated using the following procedure to ensure that treatment assignment is unbiased and concealed from subjects and investigator staff. A subject randomisation list will be produced by ICON Biostatistics using a validated system that automates the random assignment of subject numbers to randomisation numbers. These randomisation numbers are linked to the different treatment regimens, which in turn are linked to medication numbers. A separate medication list will be produced using a validated system that automates the random assignment of medication numbers to packs containing the investigational drug.

Subjects, investigational staff, persons performing the assessments and data analysts (other than those described below) will remain blind to the identity of the treatments [REDACTED] from the time of randomisation until database lock. In order to maintain the blind described above, testosterone measurements will be blinded to site and sponsor staff and monitoring will be performed by an independent unblinded physician. The interim analysis will be performed by an independent unblinded committee (see [Section 16.3](#)).

The blind will be maintained using the following methods:

1. Randomisation data will be kept strictly confidential until the time of blinding, and will not be accessible to anyone involved in the study

2. The identity of the treatments will be concealed by the use of investigational treatment that is identical in packaging, labelling, schedule of administration and appearance.

Should a situation arise where unblinding is required, the investigator at that site may perform immediate unblinding without the need for communication with the sponsor (see [Section 10.3](#)).

